9 STATISTICAL CONSIDERATIONS

The study is a post-market clinical follow-up study. Given the observational nature of the study a sample size calculation was not performed. The total enrollment goal of 120 subjects was selected in an effort to create a generalizable sample that is large enough to provide sufficient data on safety and performance. Outcomes recorded at specific time points will be analyzed according to standard measures of descriptive statistics. The number of dropouts and withdrawals will be presented. Interim analyses may be conducted based on regulatory request. After completion of the study, a final report encompassing all study data will be generated.

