9.1 Sample Size

Sample size calculations were based on a one-sided Z-test for two proportions. The study was powered to detect a difference in the proportion healed in the treatment and control groups. The healing rate on the postoperative MRI in the treatment group was assumed to be 75%, and in the control group, 40%. Further assumptions included a one-sided alpha level of 0.025 and 90% power. Under these assumptions, 40 subjects per group are required. To account for a potential dropout of up to 33%, this study will enroll 120 total subjects (60 per group).

Sample size was estimated using PASS 2021 Power Analysis and Sample Size Software (2021). NCSS, LLC. Kaysville, Utah, USA, ncss.com/software/pass.

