9.5 Analysis of Study Outcomes

9.5.1 Primary Outcomes

The primary outcome of difference in healing rates between groups will be assessed under the following hypothesis:

$$H_0: \pi_T - \pi_C \leq 0$$

$$H_a: \pi_T - \pi_C > 0$$

Where π_T is the healing rate at six months in the treatment group (RCR + DAA) and π_C is healing rate in the control group (non-augmented RCR) at six months. The difference in rates between groups will be summarized, along with a 95% confidence interval.

A chi-square test will be performed to obtain a p-value of the comparisons between groups. A one-sided p-value of <0.025 will be used to define success of the hypothesis (i.e., postoperative healing is improved with the addition of DAA).

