9.5.2 Secondary Outcomes

The following secondary outcomes will be assessed using descriptive statistics, with results presented by group at Pre-op/Baseline and each follow-up.

- American Shoulder and Elbow Surgeons Score (ASES)
- Single Assessment Numeric Evaluation score (SANE)
- Visual Analog Scale (VAS) for pain
- Veterans RAND Health Survey (VR-12)

Changes from pre-operative values will also be summarized by group. Changes between groups may be compared using two-sample t-tests.

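### Does the opening of section 9, which calls the study observational and denies a sample size calculation, undermine the randomised, powered design?

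*Combined protocol and SAP*

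**What the plan says.** The opening paragraph of section 9 makes three statements that bear on this point:

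- On design and sizing: "Given the observational nature of the study a sample size calculation was not performed".
- On the enrolment target: "The total enrollment goal of 120 subjects was selected in an effort to create a generalizable sample", with sufficient data on safety and performance given as the further aim.
- On analysis: "Outcomes recorded at specific time points will be analyzed according to standard measures of descriptive statistics".

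Section 9.1 follows directly and says: "Sample size calculations were based on a one-sided Z-test for two proportions". It adds: "The study was powered to detect a difference in the proportion healed in the treatment and control groups". It gives healing rates of 75% and 40%, a one-sided alpha of 0.025, 90% power, 40 subjects per group, an allowance for up to 33% dropout, a total of 120 (60 per group), and the software used.

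Section 9.5.1 states directional hypotheses on the six-month healing rate, a chi-square test and a decision rule: "A one-sided p-value of <0.025 will be used to define success of the hypothesis". For the patient-reported outcomes, section 9.5.2 adds an optional comparison: "Changes between groups may be compared using two-sample t-tests".

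On design, the title calls the study randomised, section 3.1 calls it prospective and randomised, section 4.4 specifies computer-generated allocation during surgery, and section 9.4 refers to the randomised subjects. Section 4.1 gives the enrolment goal as 120, with 60 per group.

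**The concern.** Two adjacent parts of the statistics chapter give accounts that cannot both be true. A study that allocates treatment by computer-generated randomisation is not observational. A study with a stated test, event rates, alpha, power and dropout allowance has had a sample size calculation. The post-market label does not remove the conflict, because the title itself describes a study that is both randomised and post-market.

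The conflict would matter if it left the basis for the sample size, or the standing of the primary comparison, in doubt. Section 12 requires the final report to describe the methodology and design. A report author who relied on the opening of section 9 alone would present a randomised comparison with a preset success rule as an observational study of convenience size. A reader could then ask whether the primary test was planned in advance. It could also be asked whether a general statement about descriptive statistics displaces the test in 9.5.1.

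**Working it through.** **Step 1. Does the calculation in 9.1 stand by itself?** The inputs, all from section 9.1, are a treatment rate of 0.75, a control rate of 0.40, a one-sided alpha of 0.025 (z = 1.960), power of 0.90 (z = 1.282) and equal allocation. The mean rate is (0.75 + 0.40)/2 = 0.575.

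For the Z-test with pooled variance and no continuity correction:

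n per group = [1.960 × √(2 × 0.575 × 0.425) + 1.282 × √(0.75 × 0.25 + 0.40 × 0.60)]² / 0.35²

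= (1.3702 + 0.8379)² / 0.1225 = 4.876 / 0.1225 = 39.80, so 40 per group.

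Normal-approximation power at 40 per group is 90.1%. The plan's figure of 40 is reproduced.

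**Step 2. Does 40 lead to 120?** Dropout of 33% gives 40 / (1 − 0.33) = 59.7, so 60 per group and 120 in total. In the other direction, 60 × 0.67 = 40.2 evaluable per group. The plan's figure of 120 is reproduced.

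**Step 3. Does the result depend on the variant of the test?** With unpooled variance the formula gives 36.67, so 37 per group. With a continuity correction it gives 46. Section 9.5.1 does not say whether its chi-square test is corrected. Exact power under the 9.1 rates is:

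| Evaluable per group | Uncorrected | Continuity-corrected |
|---|---|---|
| 40 | 90.7% | 86.2% |
| 60 | 98.0% | 96.8% |

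This spread comes from the wording of 9.5.1. It would be the same whether or not the opening sentence of section 9 existed.

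**Step 4. Set the statements side by side.**

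| Item | Opening of section 9 | Elsewhere | Conflict? |
|---|---|---|---|
| Design | Observational | Randomised (title, 3.1, 4.4, 9.4) | Yes |
| Sample size calculation | Not performed | Performed and reported in full (9.1) | Yes |
| Total enrolment | 120 | 120 (4.1, 9.1) | No |
| Reason for 120 | Generalisability, safety and performance data | Power plus dropout (9.1) | Not in itself: one number can serve both aims |
| Analysis | Descriptive statistics | Chi-square test with success rule (9.5.1); optional t-tests (9.5.2) | No: the general sentence does not say that only descriptive statistics will be used |

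**Step 5. What would be done differently under each reading?** Allocation follows 4.4. Enrolment stops at 120 under either account. The primary test, its direction and its threshold come from 9.5.1, which the opening paragraph does not mention or modify. No operational or analytical step changes.

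**The case for a change.** The strongest case for acting is that the opening paragraph is current text, sits at the head of the statistics chapter, and is contradicted by the next subsection. Nothing in the document says that 9.1 takes precedence. If the paragraph is leftover wording from a general post-market template, which is plausible but not shown, that is a reason to correct it. The correction would be short, and it is better made before results are known than afterwards.

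Much of this stands. The words on observational design and on the missing calculation are wrong for this trial. The arithmetic also cannot show which came first, the number 120 or the calculation that yields it.

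The step to a needed change does not stand. Harm would require a report author to follow one sentence against the title, sections 3.1, 4.4 and 9.4, and the detailed text of 9.1 and 9.5.1. The primary test is prespecified in 9.5.1 with hypotheses and a threshold, so its standing does not rest on how the chapter is introduced. The claim that the opening contradicts the success rule also fails: a study can lack a sample size calculation, or report most outcomes descriptively, and still have a prespecified test.

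**Conclusion.** The contradiction exists and is clerical. It is confined to one sentence: the study is randomised, and a sample size calculation was done and reproduces at 40 evaluable per group and 120 enrolled. The generalisability aim and the general statement on descriptive statistics can both stand beside 9.1 and 9.5.1.

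The effect on sample size, alpha, endpoint, primary test and conclusion is zero. Any analyst reading the whole chapter would work from 9.1 and 9.5.1, because they are specific, agree with sections 3.1, 4.1 and 4.4, and contain everything needed to act. No change to the plan follows.

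The conclusion assumes that the trial is run as 4.4, 9.1 and 9.5.1 describe. It does not depend on whether 120 was fixed before or after the calculation, because the number is the same either way.

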9.1 Sample Size

Sample size calculations were based on a one-sided Z-test for two proportions. The study was powered to detect a difference in the proportion healed in the treatment and control groups. The healing rate on the postoperative MRI in the treatment group was assumed to be 75%, and in the control group, 40%. Further assumptions included a one-sided alpha level of 0.025 and 90% power. Under these assumptions, 40 subjects per group are required. To account for a potential dropout of up to 33%, this study will enroll 120 total subjects (60 per group).

Sample size was estimated using PASS 2021 Power Analysis and Sample Size Software (2021). NCSS, LLC. Kaysville, Utah, USA, ncss.com/software/pass.

9.2 Descriptive Statistics

Continuous data will be summarized with mean, standard deviation, median, minimum, maximum, and number of evaluable observations. Categorical data will be summarized with frequency counts and percentages. Confidence intervals may be presented, where appropriate, using the t-distribution for continuous data and normal approximation for binomial data (unless otherwise noted).

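### The only interval method named for proportions, the normal approximation, fails at low counts; any adverse-event or sparse Sugaya interval needs another method (minor)

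*Combined protocol and SAP*

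**What the plan says.** Section 9.2 (Descriptive Statistics) covers intervals in one sentence. It makes them optional, limits them to cases where they suit, and says how they are formed: "using the t-distribution for continuous data and normal approximation for binomial data (unless otherwise noted". Nothing in sections 9.3 to 9.5 notes a different method for proportions.

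Section 9.5.1 makes one firm commitment to an interval: "The difference in rates between groups will be summarized, along with a 95% confidence interval". It names no method, so the 9.2 default applies. Next to it stand the test, "A chi-square test will be performed to obtain a p-value of the comparisons between groups", and the rule, "A one-sided p-value of <0.025 will be used to define success of the hypothesis". Whether the chi-square carries a continuity correction is not stated.

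Section 9 contains no adverse-event analysis, and section 9.5.3 reports the Sugaya types as frequency distributions only. The introduction to section 9 nevertheless describes the enrolment goal as "large enough to provide sufficient data on safety and performance", so event proportions by arm are likely to be tabulated.

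**The concern.** The normal approximation (read here as the Wald interval, its usual meaning) puts the observed proportion p̂ into its own standard error. When no event is seen, the standard error is zero and the interval collapses to a point. With one to three events in 60, the lower limit is negative. Arms here are 60 enrolled and about 40 evaluable on MRI. The protocol calls the study minimal risk (section 7) and the graft-specific risks minimal (section 3.2.1), so counts near zero are plausible.

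At stake is the honesty of the error bars in the final report. A zero-width interval for graft reactions would read as proof of absence, when 60 subjects cannot exclude a rate of nearly 6%.

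A smaller question arises for the primary endpoint. The Wald interval uses the unpooled variance and the chi-square the pooled variance, so the two can disagree at the margin.

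**Working it through.** **Inputs.** Section 9.1: healing rates ("The healing rate on the postoperative MRI in the treatment group was assumed to be 75%, and in the control group, 40" per cent), error rates ("Further assumptions included a one-sided alpha level of 0.025 and 90% power"), 40 per group, inflated to 60 for 33% dropout. The documents give no adverse-event rate, so the 1% to 5% range is an assumption. Unequal evaluable arms (35 and 45; 42 and 38) are also assumptions.

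**The plan's own figure.** With pooled p = 0.575:

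n = [1.960·√(2·0.575·0.425) + 1.2816·√(0.75·0.25 + 0.40·0.60)]² / 0.35² = (1.370 + 0.838)² / 0.1225 = 39.8, so 40 per group.

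40/0.67 = 59.7, so 60. Both figures reproduce. This is the uncorrected Z-test; a continuity-corrected calculation would need 46.

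**Single proportions at low counts.** Wald: p̂ ± 1.96·√(p̂(1−p̂)/n).

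- 0/60: 0% to 0%. The exact (Clopper-Pearson) upper limit is 1 − 0.025^(1/60) = 5.96%; Wilson gives 6.02%.
- 1/60: Wald −1.6% to 4.9%; Clopper-Pearson 0.04% to 8.9%.
- 0/40: Wald 0% to 0%; exact upper limit 1 − 0.025^(1/40) = 8.8%.

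Coverage is the sum of binomial probabilities over the counts whose interval contains the true rate:

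| True rate (assumed) | P(0 events), n=60 | Wald, n=60 | Wilson, n=60 | Clopper-Pearson, n=60 | Wald, n=40 |
|---|---|---|---|---|---|
| 1% | 54.7% | 45.2% | 97.8% | 97.8% | 33.1% |
| 2% | 29.8% | 70.1% | 96.8% | 99.3% | 55.3% |
| 3% | 16.1% | 83.7% | 96.6% | 99.1% | 70.3% |
| 5% | 4.6% | 80.6% | 97.0% | 99.0% | 86.8% |

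Most of the loss is the zero-event arm, whose interval always misses. The dip at 5% and n=60 arises because the upper limit for 1/60 (4.9%) also falls just short.

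**Primary difference: coverage.** Enumerating all tables at 75% versus 40%, Wald coverage is 94.5% at 40 per arm and 94.9% at 60 per arm.

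**Primary difference: agreement with the test.** At 40 per arm, only two tables favouring treatment disagree with the uncorrected chi-square: 32 versus 24 healed, and 16 versus 8. For 32/40 versus 24/40:

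- Pooled SE = √(0.7·0.3·2/40) = 0.1025; z = 0.20/0.1025 = 1.952; one-sided p = 0.0255, so the rule fails.
- Unpooled SE = √(0.8·0.2/40 + 0.6·0.4/40) = 0.100; Wald interval 0.4 to 39.6 points.
- Score interval: −0.1 to 38.8 points, in line with the test.

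Probability that the Wald interval excludes zero in favour of treatment while the test fails:

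| Evaluable (treatment/control) | True rates | Uncorrected | Continuity-corrected |
|---|---|---|---|
| 40/40 | 75% vs 40% | 0.06% | 4.6% |
| 40/40 | 80% vs 60% | 2.0% | 11.2% |
| 35/45 | 75% vs 40% | 1.3% | 5.7% |
| 35/45 | 80% vs 60% | 4.4% | – |

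With equal arms the disagreement runs only this way, because the pooled variance is never the smaller. With unequal arms it can reverse: at 36/45 versus 21/35 the unpooled variance is 0.16/45 + 0.24/35 = 0.01041, marginally above the pooled 0.7125·0.2875·(1/45 + 1/35) = 0.01040.

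**The case against.** The strongest reply is that section 9.2 is permissive. Intervals are optional, limited to where they suit, and open to exceptions. A zero count is an obvious case for leaving the normal approximation out. No section promises an interval for adverse events or Sugaya types. A reader might infer that the safety table will print a 0% to 0% interval; the documents do not support that, and the harm arises only if such intervals are produced. The event rates behind the coverage figures are also not the plan's. All of this stands. It does not remove the gap: the only method named is the one that fails at low counts, and the choice of another is left until the data are in hand.

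A reader might also infer that the primary interval threatens to contradict the primary test. That reading is too strong. At the planned rates with 40 per arm, disagreement with the uncorrected test occurs in 0.06% of trials. The 2.0% figure needs true rates equal to the proportions in one of the two discordant tables. Section 9.5.1 defines success by the p-value alone, so a discordant interval changes no decision. The larger potential source of disagreement is the unstated continuity correction.

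**Conclusion.** Minor, and conditional. Section 9.2 names one interval method for proportions. If it is applied to low counts, nominal 95% intervals at n=60 cover 45% to 84% of the time for assumed true rates of 1% to 5%, and collapse to zero width when no event is seen. The committed interval, for the primary difference, is adequate near the planned rates. Its disagreement with an uncorrected chi-square ranges from 0.06% of trials (40 per arm, planned rates) to about 4% (35 versus 45 evaluable, 80% versus 60%) and does not touch the success decision.

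The conclusion rests on reading the normal approximation as the Wald interval, on the assumed event rates, and on the assumed splits of evaluable subjects.

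**What to change.** In section 9.2, keep the t-distribution for continuous data and replace the clause on binomial data: single proportions get Wilson or Clopper-Pearson 95% intervals, including any adverse-event or Sugaya proportions for which intervals are shown.

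In section 9.5.1, name the score interval for the difference without the N/(N−1) variance factor (Mee type), and state that the chi-square is Pearson's without continuity correction. At a difference of zero this interval uses the same pooled variance as the test, so its lower limit exceeds zero exactly when one-sided p < 0.025. The uncorrected test also matches the Z-test calculation that gave 40 per group.

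The Miettinen-Nurminen version is not the right choice if agreement is the aim, because it includes that factor. For 31/42 versus 20/38 the pooled z is 0.2118/0.1076 = 1.968, which passes. Dividing by √(80/79) gives 1.955, so that interval contains zero. At 42 versus 38 evaluable and 75% versus 40%, this happens in 2.0% of trials.

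The cost is two sentences of wording and intervals that are asymmetric and, at low counts, slightly wider. The sample size and success rule do not change.

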9.3 Handling of Missing Data

All attempts will be made to limit the amount of missing data. Unless otherwise specified, no attempt will be made to impute missing data. The number of subjects that contribute data to each analysis will be stated in the final report. In cases of subject withdrawal, data recorded from subjects up to the time of withdrawal will be reported and analyzed. The number of dropouts and withdrawals will be presented.

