3 STUDY DESIGN

3.1 Study Design and Rationale

This is a prospective randomized study comparing the outcomes of patients undergoing rotator cuff repair with dermal allograft augmentation (DAA) or a control group without dermal allograft. Patient outcomes will be collected and compared between the two cohorts at two years postoperative and will include a range of subjective and functional outcomes and radiographic imaging. All patients undergoing primary rotator cuff repair surgery will be invited to be part of the study after pre-operative inclusion/exclusion criteria have been met.

Hypothesis: Patients undergoing rotator cuff repair surgery will experience improved tendon healing with the use of CuffMend™ dermal allograft augmentation.

The purpose of this study is to compare postoperative healing of large and massive rotator cuff tears with preoperative MRI confirmed fatty infiltration stage II and higher repaired with or without dermal allograft augmentation (DAA).

The outcome measures were selected based on the recommendations of the American Academy of Orthopaedic Surgeons (AAOS) and literature review.

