3.3 Study Objectives and Outcome Measures

3.3.1 Study Objectives

The purpose of this study is to compare postoperative healing of large and massive rotator cuff tears with preoperative fatty infiltration stage II and higher repaired with or without DAA.

Primary Hypothesis: Improved postoperative healing with the addition of CuffMend™ DAA, assessed with MRI Imaging

Secondary Hypothesis: Improved Patient-Reported Outcomes and range of motion with the addition of CuffMend™ DAA

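### The two-year comparison of ASES, SANE, VAS and VR-12 uses available cases only; where groups are compared, a repeated-measures model would use the scores already collected and rest on a weaker missing-data assumption

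*Combined protocol and SAP*

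**What the plan says.** Three parts of the combined protocol and SAP bear on this.

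- **Section 9.3, Handling of Missing Data.** "Unless otherwise specified, no attempt will be made to impute missing data", and no exception for the patient-reported scores appears elsewhere. For those who leave: "In cases of subject withdrawal, data recorded from subjects up to the time of withdrawal will be reported and analyzed". Section 9.3 also says "The number of subjects that contribute data to each analysis will be stated in the final report", so varying denominators are expected.
- **Section 9.5.2, Secondary Outcomes.** The four scores are summarised descriptively, "with results presented by group at Pre-op/Baseline and each follow-up". On the between-group comparison it says only: "Changes between groups may be compared using two-sample t-tests". The test is optional and no visit is named.
- **Sections 3.1 and 3.3.1.** "Patient outcomes will be collected and compared between the two cohorts at two years postoperative". The stated aim for these scores is directional: "Secondary Hypothesis: Improved Patient-Reported Outcomes and range of motion with the addition of CuffMend™ DAA".

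Section 6 schedules ASES, SANE and VR-12 at baseline, 26 weeks, one year and two years, with VAS also at two and six weeks. Section 9.1 sets the enrolment: "To account for a potential dropout of up to 33" per cent, 120 subjects are enrolled. Under section 4.3, subjects withdrawn after treatment are not replaced. No longitudinal model, missing-data assumption or sensitivity analysis is given for the scores.

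**The concern.** A subject without a two-year score has no two-year change, and with no imputation is absent from any t-test at that visit. The 26-week and one-year scores of that subject predict the missing value but play no part in the two-year difference.

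This matters because the plan's own premises make a neutral pattern of loss uncertain. Section 9.1 assumes 60% unhealed in controls against 25% with augmentation (100% minus the stated 40% and 75%). Section 2.1 relies on a link between healing and function. The MRI comes at 26 weeks, before the last two score visits, so its result could be known before later follow-up is completed or abandoned. If subjects doing badly leave more often, and more of them are controls, the two-year difference is understated. If satisfied subjects leave instead, the direction can reverse.

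**Working it through.** **The plan's own figure.** With 75% v 40%, one-sided alpha 0.025, 90% power and a pooled Z-test, the mean rate is 0.575 and

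n = [1.960 × √(2 × 0.575 × 0.425) + 1.2816 × √(0.75 × 0.25 + 0.40 × 0.60)]² / 0.35² = 39.80, so 40 per group.

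Allowing for dropout, 40 / (1 − 0.33) = 59.7, so 60 per group. Both stated figures reproduce. If 33% lack a two-year score, about 40 of 60 per group enter a two-year t-test and about 20 do not.

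**Assumptions for the bias.** The documents give no SD, effect size or between-visit correlation for the scores. In SD units, with higher scores better, let ρ be the correlation between the one-year and two-year scores. Let loss before two years depend on the one-year score with log-odds 1 per SD worse.

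**Formula.** Let s be the mean one-year score of those who stay minus that of the whole arm. The available-case two-year mean of that arm is then too high by ρ × s, and the bias in the difference (augmented minus control) is ρ × (s_augmented − s_control). With no true effect, s is about 0.28 at 33% loss, 0.17 at 20% and 0.09 at 10%.

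**Results** (simulation with 2,000,000 per arm):

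| Scenario | ρ = 0.4 | ρ = 0.6 | ρ = 0.8 |
|---|---|---|---|
| No effect, same mechanism, 33% lost in each arm | 0.00 | 0.00 | 0.00 |
| Effect 0.5 SD, same mechanism (33% control, 24% augmented lost) | −0.03 | −0.04 | −0.05 |
| No effect, 33% control v 20% augmented lost | −0.04 | −0.06 | −0.08 |
| No effect, 33% lost in each arm, score-related in control only | −0.11 | −0.17 | −0.22 |

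- In the first row each arm's mean is still too high, by 0.11 to 0.22 SD. The two errors cancel in the difference.
- In the second row, dividing the unrounded biases by 0.5 gives 0.027 / 0.5 = 5% to 0.053 / 0.5 = 11%, or 6% to 10% from the rounded figures (0.03 and 0.05).
- An estimate that uses the one-year score brings the bias to about 0.00 in every row.
- With 60 per arm and ρ = 0.6, the type I error of a nominal two-sided 5% t-test is 4.6% (same mechanism), 6.1% (33% v 20%) and 11.5% (control only).

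**A second set of assumptions, in points.** There were 60 per arm, with healing 75% v 40%, change SD 20 and unhealed shoulders 10 to 20 points lower. The true difference is therefore 0.35 × 10 = 3.5 to 0.35 × 20 = 7.0 points. Correlation was 0.5 to 0.7. In all 33% were missing at two years: 11% lost at random before 26 weeks, and 22% lost later with odds 2.7 to 4.5 times higher per SD worse last score. Over 4,000 simulated trials per scenario the available-case difference was 11% to 22% too small, for example 5.5 instead of 7.0 points. A separate simulation under the same assumptions gave 10% to 21%. The likelihood estimate from all visits was within 3% of the truth. With dropout unrelated to outcome neither estimate was biased, and the available-case variance was 1.07 to 1.20 times that of the all-visit estimate.

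**The case against.** A reader might infer that section 9.3 makes a promise that 9.5.2 breaks. The text does not support that. Section 9.3 does not say that scores recorded before withdrawal enter the two-year test; they are analysed at the visits attended, and varying denominators are foreseen.

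A reader might also infer that loss of poorer-scoring subjects always biases the comparison. It does not. With no effect and one mechanism in both arms, the bias is zero and type I error stays near 5%.

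Other objections stand in part.

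- **The test is optional and names no visit.** This is true, and the only success criterion is for six-month MRI healing. But if the two-year comparison in section 3.1 is made, this is the only method offered, and descriptive means by visit share the limitation.
- **The size rests on outside inputs.** This is also true. The 33% is an upper allowance in the MRI sample size, not a forecast of score loss, and nothing in the documents suggests that score-related loss is confined to controls. The largest figures (−0.22 SD, 11.5% type I error) are therefore an outer bound of the cases examined.
- **The bias is modest against sampling error.** In the example it is 7.0 − 5.5 = 1.5 points, against a standard error of about 20 × √(2/40) = 4.5 points. It also runs against the sponsor's hypothesis.
- **The model's good performance is built in.** Simulated dropout depended only on observed scores or was random, which is the condition under which the model works. Its accuracy under other dropout was not shown.

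**Conclusion.** The point holds as a limitation of the analysis, not as a contradiction in the plan. Any two-year comparison of the four scores is an available-case analysis that leaves earlier post-operative scores unused. The difference can be biased when score-related dropout differs by arm, or when a true effect exists and dropout depends on score. The second condition is close to what the plan itself expects.

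The size cannot be fixed from the documents. It is about 10% to 22% attenuation under the stronger dropout assumptions, about 6% to 10% with a 0.5 SD effect and milder dropout, and nil with no effect and a common mechanism. The primary comparison of MRI healing at six months is not affected. The change is worth making because it is cheap, needs a weaker missing-data assumption, and loses essentially nothing if dropout is unrelated to outcome.

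**What to change.** In section 9.5.2, state that when groups are compared on ASES, SANE, VAS or VR-12, the method is one mixed model for repeated measures per score:

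- Outcome: change from the pre-operative value at all scheduled post-operative visits.
- Terms: arm, visit and arm-by-visit, with an unstructured within-subject covariance.
- Subjects: everyone randomised with at least one post-operative score.
- Report: the arm difference with a 95% confidence interval at each visit, including two years.

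Keep the available-case summaries as descriptive tables. Add a cross-reference in section 9.3 saying that this model is how scores recorded before withdrawal inform later comparisons.

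The cost is SAP wording and slightly more analysis work, with no new visits, data or subjects. Two limits should be stated. Subjects with only a pre-operative score still do not contribute. The model also assumes that missingness is explained by observed scores, so it does not protect against dropout driven by deterioration that was never recorded.
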